5.4.2.1.2 Viral Resistance Measurements

In this trial, RASs are defined as specific genetic substitutions that generate viral proteins that maintain function, but have reduced susceptibility to a DAA. As the presence of certain HCV RASs can lead to treatment failure, they are one of the most important considerations when treating with a DAA. Those genetic substitutions that impact efficacy outcomes may be present at baseline (ie, prior to therapy), or they may be treatment-emergent (ie, not detected at baseline, but which emerge and are selected over the course of therapy).

Blood samples for viral resistance assays are collected at:

- **Screening**: Testing will be done to assess for the presence of NS5A and NS3 RASs that have been associated with reduced efficacy for NS5A compounds (eg, ledipasvir, daclatasvir, EBR) or protease inhibitors (eg, simeprevir, boceprevir, telaprevir, GZR). In GT1a-infected participants, presence of NS5A RAS at amino acid position 28, 30, 31, and/or 93 will be used for enrollment criteria as outlined in inclusion/exclusion.
- **Virologic failure and/or selected follow-up visits**: To better understand the emergence and natural history of RASs in association with virologic failure, samples will be obtained at virologic failure confirmation visits, Follow-up Week (FW) 4, FW12, and FW24. RASs will be assessed for any participant who has detectable virus above 1000 IU/mL and has met an HCV virologic failure criteria. Blood samples for resistance testing are also collected at all visits following confirmation of virologic failure to the end

of the trial. To limit the risk of RASs, participants are not allowed to have monotherapy with EBR or GZR in this protocol.

Participants who have met virologic failure criteria, will be offered follow-up in a 3-year long-term follow-up protocol, MK-5172 Protocol 017, to determine the persistence of RASs and to determine time course of reversion to wild-type.

5.4.2.2 Palatability and Acceptance Assessment Endpoint

Adherence to treatment for chronic HCV infection is necessary for participants to achieve SVR. Palatability may play an important role in adherence to HCV treatment in the pediatric population. Palatability is an important element in the determination of acceptability, and encompasses a product's smell, taste, aftertaste, and texture. Acceptability, including palatability, of EBR/GZR will be assessed in all participants using the Palatability Acceptance Assessment (PAA). In previous studies, the most commonly reported assessment measured palatability preference using a visual analog scale that was modified by including a facial hedonic scale (FHS; facial expression scale depicting various degrees of pleasure) [Thompson, C., et al 2015]. The five-point FHS for taste is one of the most frequently reported types of palatability assessments used in pediatric clinical trials.

5.4.2.3 Safety Endpoints

5.4.2.3.1 General Safety

The safety and tolerability of EBR in combination with GZR are assessed by a clinical evaluation of AEs and inspection of other study parameters including vital signs, physical examinations, and standard laboratory safety tests at appropriate time points as specified in the SoA. Adverse events are graded and recorded according to Section 9.3. Participants may be asked to return for unscheduled visits in order to perform additional safety monitoring.

5.4.2.3.2 Late ALT Elevations and Hepatic ECI Resulting in a Pause in Enrollment

As discussed in Section 3.2.3.2, ALT elevation is a safety signal associated with increased GZR exposures. In this trial, it is expected that the safety profile should match adults. Therefore, safety of an Age Cohort will be based on the following criteria.

If ≥ 3 participants receiving a given EBR/GZR dose in an Age Cohort experience any of the following, allocation of new participants into the Age Cohort will be paused. Participants that are tolerating treatment with that study drug combination may continue to receive study therapy, but no additional participants will be enrolled until the Sponsor has reviewed all safety and PK data of participants receiving the drug combination.

- ALT or AST increases to >500 IU/L and is confirmed with repeat test immediately.
- ALT or AST increases to $>3\times$ baseline and/or nadir, is >100 IU/L, and there is a simultaneous increase in total bilirubin $>2\times$ upper limit of normal (ULN) and/or international normalized ratio (INR) is increased from the baseline value and is >1.5 (unless the participant is on anticoagulation).

- ALT or AST increases to $>3\times$ baseline and/or nadir, is >100 IU/L, and there is a simultaneous increase in total bilirubin $>2\times$ ULN and/or INR is increased from the baseline value and is >1.5 (unless the participant is on anticoagulation).
- The participant's alkaline phosphatase increases to $>3\times$ ULN, there is a simultaneous increase in total bilirubin $>2\times$ ULN and other causes of elevated alkaline phosphatase are excluded.
- The participant's alkaline phosphatase increases to $>5\times$ ULN and other causes of elevated alkaline phosphatase are excluded.
- The participant has a life-threatening clinical or laboratory AE or an AE that results in or prolongs an existing inpatient hospitalization, or death, that is assessed to be study drug-related.

In the event this pause criterion is met, the eDMC will be notified and enrollment into the Age Cohort will be paused and PK-PD analysis will be performed to re-assess and identify an appropriate safety boundary for the pediatric population.

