3.2.3.2 Modeling and Simulation in Adults

Population PK, PK/PD, and PBPK models have been developed for EBR and GZR in support of the adult filings.

GZR is associated with exposure-dependent alanine aminotransferase (ALT) or aspartate aminotransferase (AST) elevations that typically occur around TW 8-10. The efficacy endpoint for EBR and GZR of SVR₁₂ is also exposure-dependent. Logistic regression PK/PD models for safety and efficacy have been established using adult data. During PK/PD model development, AUC was found to be the most predictive PK parameter for both safety and efficacy. Using the PK/PD models, the therapeutic bounds, based on AUC, were defined for EBR [0.5, 2.0] and GZR [0.4, 5.0].

Based on the EBR and GZR population PK models (N=3214 total patients and healthy participants), the impact of various intrinsic factors on the plasma PK of EBR and GZR were determined and are demonstrated in the forest plot in [Figure 1](#). Several intrinsic factors affected EBR and/or GZR PK, but most changes were within the clinical comparability bounds, and therefore not clinically relevant. For example, low body weight (~37-66 kg) had an ~20% increase in AUC for both EBR and GZR, but the increase was well within the therapeutic window for both compounds. EBR/GZR are contraindicated in patients with Child-Pugh B and C cirrhosis.

PBPK models for EBR and GZR were previously developed, which incorporated the key absorption, distribution, metabolism, and excretion (ADME) and PK properties for both compounds (eg, OATP1B saturation for GZR) [M&S Analysis Rpt 2015][M&S Analysis Rpt 2015]. This modeling provided supportive mechanistic evidence and interpretation for the effect of intrinsic factors (eg, HCV infection, cirrhosis, Asian ethnicity) on the PK of EBR and GZR.

These data and models supported the approval of EBR/GZR in adults infected with HCV GT1 and/or 4 and will be updated and used to select appropriate doses for the pediatric population.

[figure not shown]

Figure 1 Impact of Intrinsic Factors on the AUC of EBR and GZR

The shaded area of [Figure 1](#) represents the region of no clinically relevant effect.

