Enrollment into Mini Age Cohort 2 will follow Mini Age Cohort 1 by 2 to 3 weeks to allow time to review Day 1 PK (AUC) in a minimum of 6 participants of Mini Age Cohort 1 before enrolling Mini Age Cohort 2. The Week 4 intensive PK from the first two Mini Age Cohorts (N=~14), in addition to the Day 1 and Week 8 sparse PK, will be used to update the population PK and PBPK models to select optimal doses for Mini Age Cohort 3 and Expanded Age Cohort 1.

2. Mini Age Cohort 3 and Expanded Age Cohort 1 will enroll in the second wave of participants after optimal doses have been selected based on PK modeling results from the first wave of participants.
 - a. Expanded Age Cohort 1 will enroll following completion of the PK modeling analyses; dosing will use the proposed dose for each component, EBR and GZR, and dose recommendation by weight bands will be used.
 - b. Mini Age Cohort 3: PK modeling and simulation will be used to propose dosing for each component, EBR and GZR. Dose recommendation by weight bands will be used for Mini Age Cohort 3.

Data from the three Mini Age Cohorts and from Expanded Age Cohort 1 will be used to update the population PK and PBPK models in order to propose doses for Expanded Age Cohorts 2 and 3.

3. Expanded Age Cohorts 2 and 3 (Expanded Age Cohort 2/3)

- a. Expanded Age Cohorts 2 and 3 are combined as a single group Age Cohort 2/3. This age cohort will enroll following completion of the updated PK modeling analyses that incorporates PK data from all previous cohorts, including all 21 participants from the three Mini Age Cohorts and all 15 participants from Expanded Age Cohort 1. Dosing of Expanded Age Cohort 2/3 will use the modeling and simulation proposed dose for each component, EBR and GZR.

While age cohorts are used for the purposes of enrollment, dose recommendations by weight bands will be used for Mini Age Cohort 3 and the Expanded Age Cohorts. Weight bands will be determined based on the PK analyses.

Following the conclusion of this study and the Clinical Study Report (CSR) for the study, a final PK model will be developed that includes all PK data from participants aged 3 years up to 18 years, in addition to relevant adult data previously collected in the program. The final model and proposed pediatric dosing regimen will be summarized in a separate report.

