PK samples will be collected in all pediatric participants according to the sampling scheme in [Table 9](#). At Day 1 (Mini Age Cohort 1 only) and TW4 (all participants), an overnight stay is recommended to obtain PK samples over a 24-hour period (intensive PK).

In order to reduce PK variability, enrollment in the Mini Age Cohorts will be limited to noncirrhotic participants of non-Asian Race who are not currently taking methadone or strong CYP3A inhibitors. The Mini Age Cohorts will also exclude participants below a weight as described in the inclusion/exclusion criteria; the Expanded Age Cohorts will enroll a broader population as described in the inclusion/exclusion criteria.

Specific procedures to be performed during the trial, as well as their prescribed times and associated visit windows, are outlined in the Trial SoA - Section 2. Details of each procedure are provided in Section 9 – Study Assessments and Procedures.

This trial will use an independent, external Data Monitoring Committee (eDMC) to monitor safety. Periodic safety analyses will be conducted and reviewed by the eDMC at regular intervals as outlined in the eDMC Charter.

The eDMC will make recommendations to the Sponsor to continue, modify, or end the trial according to Section 10 - Statistical Analysis Plan (SAP).

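### The hepatic pause rule orders a re-assessment of the safety boundary for all pediatric patients but pauses only the triggering Age Cohort, so cohorts not yet opened may start before that re-assessment is finished

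*Combined protocol and SAP*

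**What the plan says.** Section 5.4.2.3.2 sets the trigger: at least 3 participants on one EBR/GZR dose within an Age Cohort meet any listed criterion. Most criteria are hepatic. The last covers drug-related events that are life-threatening, fatal or involve hospitalization. The consequence is that "allocation of new participants into the Age Cohort will be paused". One clause addresses restart: "no additional participants will be enrolled until the Sponsor has reviewed all safety and PK data of participants receiving the drug combination". The closing sentence adds that the eDMC is notified and that enrolment into the "Age Cohort will be paused and PK-PD analysis will be performed to re-assess and identify an appropriate safety boundary for the pediatric population".

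Section 5.1 sets the conditions for opening cohorts. Mini Age Cohort 3 and Expanded Age Cohort 1 open "after optimal doses have been selected based on PK modeling results from the first wave of participants". For the last group, "Expanded Age Cohorts 2 and 3 are combined as a single group Age Cohort 2/3", and "This age cohort will enroll following completion of the updated PK modeling analyses that incorporates PK data from all previous cohorts". Sections 5.5.1.3 and 10.6.2 repeat this PK-driven sequence. None of these sections mentions the pause rule or its re-assessment.

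Section 5.5.1.1 gives the exposure check. The pediatric geometric mean AUC should be within about 2-fold of the adult value and inside the clinical bounds, EBR [0.5, 2.0] and GZR [0.4, 5.0]. Section 3.2.3.2 explains that these bounds come from adult PK/PD models.

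**The concern.** The two halves of the rule differ in scope. The pause covers one Age Cohort, while the re-assessment it triggers concerns the exposure limit for every child in the trial. A cohort that opens before the re-assessment is finished has its dose checked against bounds that the plan has just called into question.

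The timing makes this practical. Section 3.2.3.2 describes GZR-related ALT or AST "elevations that typically occur around TW 8-10". By then a Mini cohort of 7 may be full. If the trigger arises in a full Mini Age Cohort 2, the next places in that Age Cohort are in Expanded Age Cohort 2/3, which already waits for Mini Age Cohort 3 and Expanded Age Cohort 1. The pause then stops no one, while those two cohorts, one of them younger than the children who showed the signal, may open.

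**Working it through.** The plan states no operating characteristic for the pause rule, so there is none to reproduce. Two nearby safety figures in Section 10.9.3 do reproduce. The chance of at least one event among 22 at 1% is 1 − 0.99^22 = 0.198 (stated 20%). The exact upper limit for 0 of 22 is 15.4% (stated 15.4%).

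**Cohort sizes (Section 5.1, Table 2).** Mini cohorts 7, 7 and 7; Expanded 1 about 15; Expanded 2/3 about 20. Sum: 21 + 15 + 20 = 56, as stated.

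**Unopened places outside the pause.** These counts read the pause as covering one Age Cohort (Mini and Expanded together) and Expanded 2/3 as one group.

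| Trigger | Unopened places that may start | Share of 56 |
|---|---|---|
| Full Mini 2 | Mini 3 (7) + Expanded 1 (15) = 22 | 39.3% |
| Full Mini 1 | Mini 3 = 7 (Expanded 1 is held) | 12.5% |
| Age Cohort 1, after Expanded 1 and Mini 3 are full | Expanded 2/3 = 20 | 35.7% |
| Age Cohort 3, Mini 3 full | 0 (Expanded 2/3 is held) | 0% |

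In the first row, none of the 22 places belongs to Age Cohort 2, so the pause holds 0 of them.

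**Does another reading close the gap?**

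- *Trial-wide hold.* The restart clause, taken alone, names no Age Cohort. On that reading all the places in the table are held, but only until the Sponsor has reviewed the data.
- *The PK-PD analysis is part of the Sponsor review.* This is plausible, and the paused cohort would then wait for it. It does not extend the pause to other Age Cohorts unless the trial-wide reading is adopted as well.

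Only both readings together close the gap, and the text states neither.

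**How strong a signal is the trigger?** Exact (Clopper-Pearson) 95% intervals: 3 of 7 is 42.9% (9.9 to 81.6%); 3 of 22 is 13.6% (2.9 to 34.9%; the upper limit matches Table 14).

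**How often would it fire?** The documents give no rate for qualifying events, so the rates below are assumptions. P(X ≥ 3) = 1 − Σ(k = 0 to 2) C(n,k) p^k (1 − p)^(n − k). For n = 7 and p = 0.05: 1 − (0.6983 + 0.2573 + 0.0406) = 0.0038.

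| Assumed rate | n = 7 | n = 22 at one dose |
|---|---|---|
| 1% | 0.003% | 0.1% |
| 5% | 0.4% | 9.5% |
| 10% | 2.6% | 38% |

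The last column applies only if all of Age Cohort 1 receives the same dose.

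**The case against.** The strongest reply is that silence is not permission. Relating safety data to PK data is what a PK-PD analysis does, so the ordered analysis can fairly be read as part of the Sponsor's review. A reader might infer that the protocol lets the paused cohort reopen without it. The documents do not support that inference; they only leave the link unstated. This part of the reply stands, and reopening is therefore a secondary clarification.

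Second, the model update that sets second-wave doses uses Week 8 PK as well as Day 1 and Week 4 (Section 5.1), and liver chemistry is scheduled at TW8 and TW10 (Section 2). In an open-label trial the Sponsor would usually know of a first-wave trigger when choosing those doses. This also stands, but knowing of a trigger is not an obligation to wait for the re-assessment.

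Third, other safeguards apply. Because of the 2-fold criterion, a re-assessed GZR limit would change dosing mainly if it fell below about twice adult exposure. Doses cannot exceed the adult dose (Section 5.5.2), and individual stopping rules apply (Section 8.1). On oversight, "The eDMC will make recommendations to the Sponsor to continue, modify, or end the trial according to Section 10". The eDMC charter and the possible Modeling and Simulation Analysis Plan (Section 10.6.2) are not in hand and may contain restart steps. These points lower the risk. However, individual stopping rules act only after a child has been exposed, and routine eDMC review is suggested only about every 6 months (Section 10.7).

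**Conclusion.** The concern holds as a gap in scope and sequence. On the reading favoured by both sentences that impose the pause, up to about 22 of about 56 places may open before the ordered re-assessment is complete. That case is a trigger in a full Mini Age Cohort 2, and 7 of the places are for children aged 3 to under 7. The other scenarios give 7, about 20 and 0.

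A reader might take the 22 as expected exposures. They are not. They are cohort places and an upper limit, because neither the length of the pause nor the time needed for the analysis is stated. Nor do the documents show that the adult-derived bounds are unsafe for children; the rule says only that they would be re-assessed. With no event rate given, the chance of the rule firing cannot be settled either way. The point concerns what happens once it has fired. It is a cheap improvement.

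**What to change.** Add one or two sentences at the end of Section 5.4.2.3.2. Once the rule is met, no cohort not yet opened starts, and the paused Age Cohort (for Expanded Age Cohort 2/3, the merged group) does not resume, until three things are done:

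- the PK-PD re-assessment is complete;
- planned doses have been checked against its result;
- the eDMC has been given the result and the chance to advise, ad hoc if needed.

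Keep the Sponsor review. Leave any cohort already enrolling at another dose to the judgment of the Sponsor and eDMC. Event criteria and the treatment of children already enrolled do not change.

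The change puts in order an analysis and a committee that the plan already has, and the central allocation system (Section 7.3) can apply it. It needs no extra visits or samples. The cost is a somewhat longer enrolment hold, only if the rule fires. Because the last criterion is not confined to the liver, that hold could also follow three non-hepatic events.

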5.3.1 Clinical Criteria for Early Study Termination

1. The eDMC recommends termination of the trial and the Executive Oversight Committee (EOC) agrees per Appendix 3 – Committee Structure - Data Monitoring Committee, Appendix 3 – Study and Site Closure, or as stated in the DMC charter.
2. The clinical trial may be terminated early if the extent (incidence and/or severity) of emerging effects/clinical endpoints is such that the risk/benefit ratio to the trial population as a whole is unacceptable.

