9.3.4 Regulatory Reporting Requirements for SAE

- Prompt notification (within 24 hours) by the investigator to the sponsor of SAE is essential so that legal obligations and ethical responsibilities towards the safety of participants and the safety of a study treatment under clinical investigation are met.
- The sponsor has a legal responsibility to notify both the local regulatory authority and other regulatory agencies about the safety of a study treatment under clinical investigation. All Adverse Events will be reported to regulatory authorities, IRB/IECs and investigators in accordance with all applicable global laws and regulations, ie, per ICH Topic E6 (R1) Guidelines for Good Clinical Practice.
- Investigator safety reports must be prepared for suspected unexpected serious adverse reactions (SUSAR) according to local regulatory requirements and sponsor policy and forwarded to investigators as necessary.
- An investigator who receives an investigator safety report describing a SAE or other specific safety information (eg, summary or listing of SAE) from the sponsor will file it along with the Investigator's Brochure and will notify the IRB/IEC, if appropriate according to local requirements.

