10.1 Statistical Analysis Plan Summary

Key elements of the Statistical Analysis Plan (SAP) are summarized below; the comprehensive plan is provided in Sections 10.2 to 10.12.

Study Design Overview	A Phase IIb Study to Assess the Pharmacokinetics, Safety, and Efficacy of the Combination Regimen of Elbasvir (EBR)/Grazoprevir (GZR) in Pediatric Participants Aged 3 to Less Than 18 Years with Chronic Hepatitis C Infection
Treatment Assignment	This will be an open-label, non-randomized trial. Participants infected with HCV GT1a without baseline NS5A RASs at position 28, 30, 31, and/or 93; GT1b/1-other; or GT4 with HCV RNA <800,000 IU/mL; TN or PR TE (GT1 only); cirrhotic or NC, will be treated with EBR/GZR for 12 weeks within Age Cohorts (12 to <18 years, 7 to <12 years, and 3 to <7 years). Approximately 22 participants in the oldest cohort (12 to <18 years) will be enrolled. Approximately 34 participants will be enrolled in the two younger cohorts, with 12 to 22 participants in each. The total number of participants enrolled in the three cohorts will be ~56.
Analysis Populations	PK: Per-Protocol (PP) Safety: All Participants as Treated (APaT) Efficacy: Full Analysis Set (FAS) and modified FAS (mFAS)
Primary Endpoints	AUC ₀₋₂₄ , C _{max} , C _{trough} , and CL/F of EBR and GZR.
Secondary Endpoints	1. Number of participants experiencing AEs and discontinuing study drug due to AEs. 2. SVR ₁₂ (Sustained Virologic Response 12 weeks after the end of all study therapy), defined as HCV RNA <LLOQ (either TD[u] or TND) 12 weeks after the end of all study therapy.
Statistical Methods for Key Pharmacokinetic and Efficacy Analyses	Geometric means and 95% confidence intervals (CIs) will be provided for AUC ₀₋₂₄ , C _{max} , and CL/F of EBR and GZR by age cohort and dose level. The proportion of participants achieving SVR ₁₂ will be estimated using a 95% CI (via the Clopper-Pearson method). The missing data approach will be Missing=Failure (M=F).
Statistical Methods for Key Safety Analyses	Safety and tolerability will be assessed by clinical review of all relevant parameters including AEs and laboratory tests. Descriptive statistics will be provided for these safety parameters.
Interim Analyses	Periodic safety analyses will be conducted for the accruing data and will be reviewed by an eDMC at regular intervals as outlined in the eDMC charter. This will supplement routine in house medical monitoring.

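### One or two drug-related deaths or life-threatening AEs neither pause allocation nor prompt eDMC notice under Section 5.4.2.3.2

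*Combined protocol and SAP*

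**What the plan says.** Section 5.4.2.3.2 states one rule for pausing allocation. It applies when three or more "participants receiving a given EBR/GZR dose in an Age Cohort experience any of the following". The list that follows covers ALT/AST elevations, ALT/AST with bilirubin or INR changes, and alkaline phosphatase elevations. It ends with a criterion that is not hepatic: "The participant has a life-threatening clinical or laboratory AE or an AE that results in or prolongs an existing inpatient hospitalization, or death", where the event is judged related to study drug. The committee is brought in by the same count: "In the event this pause criterion is met, the eDMC will be notified and enrollment into the Age Cohort will be paused".

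The count runs per dose. Section 5.1 adds that "dose recommendations by weight bands will be used for Mini Age Cohort 3 and the Expanded Age Cohorts", so one Age Cohort may contain more than one dose.

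The other safety provisions are these:

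- Section 8.1: the affected participant must stop treatment after a drug-related life-threatening or hospitalizing event.
- Section 9.3.4: the sponsor hears of SAEs within 24 hours, safety reports are prepared for SUSARs, and "All Adverse Events will be reported to regulatory authorities, IRB/IECs and investigators in accordance with all applicable global laws and regulations".
- Section 5.1: "Periodic safety analyses will be conducted and reviewed by the eDMC at regular intervals as outlined in the eDMC Charter". Section 10.7 suggests an interval of about 6 months.
- Section 10.1, on the eDMC reviews: "This will supplement routine in house medical monitoring".
- Section 5.3.1: the trial may end if "The eDMC recommends termination of the trial and the Executive Oversight Committee (EOC) agrees", or if the risk/benefit ratio becomes unacceptable.
- Appendix 3 (Study and Site Closure): the sponsor may stop the study for safety reasons.

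**The concern.** A threshold of three suits a graded, exposure-driven signal such as ALT elevation, where single cases are expected and the pattern carries the information. It is hard to defend for a drug-related death or life-threatening event in children aged 3 to under 18, where a first case would ordinarily call for a stop and an independent look. Because both kinds of event share one count, the protocol lets allocation to the same dose continue after a first and a second such event, unless other listed events bring the total to three.

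The gap matters wherever an Age Cohort is still allocating children to that dose: chiefly the Expanded Cohorts, and Mini Cohorts that are still filling. A filled Mini Cohort already waits for PK modeling (Section 5.1). In the gap, a pause is at the sponsor's discretion, and the protocol does not require the eDMC to be told before its next periodic review.

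**Working it through.** **The plan's own figures first.** Section 10.9.3 gives a 20% chance of seeing at least one AE of 1% incidence among 22 participants: 1 − 0.99^22 = 19.8%. It gives an upper bound of 15.4% for 0 of 22; the two-sided 95% Clopper-Pearson limit is 15.4%. Both reproduce. The plan gives no operating characteristic for the pause rule.

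**Inputs.** The threshold is 3 per dose per Age Cohort (Section 5.4.2.3.2). The oldest cohort has about 22 participants and each younger cohort 12 to 22 (Section 10.1). The documents give no rate for drug-related death or life-threatening AE, so the rates below are assumptions. Calculations use the binomial distribution with independent participants and a completed cohort.

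**No assumed rate.** Two affected participants among 22 is 2/22 = 9.1%, Clopper-Pearson 95% CI 1.1% to 29.2% (the upper bound agrees with Table 14). By itself this does not fire the rule.

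**These events alone, n = 22, all on one dose.** The rule fires with P(X ≥ 3); a single-event trigger fires with P(X ≥ 1) = 1 − (1 − p)^22. For p = 5%: P(0) = 0.95^22 = 0.3235; P(1) = 22 × 0.05 × 0.95^21 = 0.3746; P(2) = 231 × 0.05² × 0.95^20 = 0.2070. So P(X ≥ 3) = 1 − 0.9052 = 9.5%, P(X ≥ 1) = 67.6%, and P(1 or 2) = 58.2%.

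| Assumed true rate | Rule fires (≥3) | Single-event trigger fires (≥1) | Exactly 1 or 2 events |
|---|---|---|---|
| 1% | 0.1% | 19.8% | 19.7% |
| 2% | 0.9% | 35.9% | 35.0% |
| 5% | 9.5% | 67.6% | 58.2% |
| 10% | 38.0% | 90.2% | 52.2% |

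**Allowing the other criteria to contribute.** Let g be the rate of these grave events and l the rate of the other listed criteria, taken as independent. Then q = 1 − (1 − g)(1 − l) is the chance that a participant counts. The probability of at least one grave event with the rule not firing is the sum over k = 1, 2 of Binom(k; 22, q) × [1 − (1 − g/q)^k].

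For g = 5% and l = 5%: q = 0.0975, g/q = 0.513, Binom(1) = 0.249, Binom(2) = 0.282, so 0.249 × 0.513 + 0.282 × (1 − 0.487²) = 34.3%.

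| g | l = 5% | l = 10% |
|---|---|---|
| 2% | 22.9% | 11.2% |
| 5% | 34.3% | 16.2% |
| 10% | 27.3% | 12.2% |

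**Effect of counting per dose.** One dose for all 22 is the case most favorable to the rule. The number of weight bands is not stated. As an illustration, with 11 participants on each of two doses, the probability that either count reaches three is 1 − [1 − P(X ≥ 3; n = 11)]². At 2%, 5% and 10% this is 0.2%, 3.0% and 17.1%. Four such events, two per dose, would not by themselves fire the rule.

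**Do the other provisions fill the gap?** Section 8.1 stops drug only for the affected child. Section 9.3.4 does not name the eDMC. Sections 5.3.1 and 10.1 and Appendix 3 set no event count and no deadline. Section 10.7 only suggests the review interval.

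The Synopsis gives about 112 weeks in total and 42.5 per participant. That leaves 112 − 42.5 = 69.5 weeks between first and last consent, or about 69.5/3 ≈ 23 weeks per enrollment wave, which is less than 6 months. This is an inference from planned durations and not a stated schedule, but it suggests that a wave could finish allocating between two reviews.

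**The case against.** The strongest reply is that eDMC operations belong in its charter, to which the protocol refers repeatedly. The charter is not among the documents and could require immediate notice of any death. That stands as a limit on the notice half of the point. It does not supply an allocation pause, which no provided text sets below three.

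Second, a first event does not pass without mandatory action: the child stops treatment, the sponsor is told within 24 hours, and SUSAR reports go out. True, and these reduce the practical risk, but none stops the next child from being allocated to that dose.

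Third, the section is headed as a hepatic rule and leads to a PK-PD reassessment, for which a per-dose count of three is reasonable. That holds for the liver criteria. The last criterion is not limited to hepatic events, however, and the section presents the list as the basis for judging an Age Cohort's safety.

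Fourth, rates of 2% to 10% may be too high. Section 3.3 describes a favorable profile in about 2,000 participants at the adult dose. At assumed rates of 0.1%, 0.5% and 1%, at least one event among 22 has probability 2.2%, 10.4% and 19.8%. Completed-cohort figures also count late events that can no longer affect allocation. Both points stand. They make the situation less likely to arise, and they equally mean that a single-event trigger would seldom interrupt the trial.

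Fifth, the 11/11 split is off-plan for Age Cohort 1, because Section 7.1 expects the Expanded Cohort to receive the same tablet as the Mini Cohort. This is correct. The illustration is relevant to a younger cohort near the top of its 12-to-22 range, or to Cohort 1 only if its dosing changes.

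**Conclusion.** The concern holds as a matter of text, with high confidence. Followed exactly, the protocol allows allocation to continue after one or two drug-related deaths or life-threatening AEs at a dose, and it requires no eDMC notice before the next periodic review. This conclusion needs no assumed event rate.

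Its size depends on rates that the documents do not give. On the assumptions above, the existing rule would seldom react to these events alone unless they were frequent, and counting per dose weakens it further where an Age Cohort is split across doses. The statement about notice is confined to the protocol and would need revisiting if the charter contains an expedited rule. This is a design choice that should be changed; no calculation in the plan is wrong.

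**What to change.** Leave the pooled rule of at least three, and its whole list, as it is. Add one sentence to Section 5.4.2.3.2: *In addition, any single study-drug-related death or life-threatening AE will pause allocation into the Age Cohort and will be notified promptly to the eDMC.* Drug-related hospitalizations that are not life-threatening would still count only toward the pooled three.

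The cost is one protocol sentence and a check that the eDMC charter agrees with it. The downside is a possible short extra pause in one Age Cohort.
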